10.2 Blood samples

Participants must attend V1, V5 and V6 after 8-10 hours of fasting having consumed only water for collection of blood samples. A small venous catheter will be inserted in one of the participant's arms for blood sampling which will be performed by a trained biomedical laboratory technician in the Clinical Biochemical Department at SDCC. The samples will be used for assessment of C-peptide, triglycerides, total cholesterol, HDL-C, LDL-C, very-low-density-lipoprotein cholesterol (VLDL-C), HbA1c, fasting glucose, haemoglobin, creatinine, albumin, potassium, sodium, alanine aminotransferase (ALAT), thyroid-stimulating hormone (TSH), leucocytes, thrombocytes, cobalamin and alkaline phosphatase according to standard procedure. No tobacco smoking is allowed in the morning before the visit. HbA1c will also be measured at the screening visit and visits V2, V3 and V4 in a non-fasting condition.

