11.5 V3: intervention, day 2 (week 12)

At visit 3 the following procedures and assessments will be performed:

- Measurement of body weight and HbA1c (non-fasting condition)
- Update of glucose- and lipid-lowering medicine
- Standard individual dietary counselling follow-up

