13.2 Statistical methods

Intention-to-treat (ITT) analysis will be performed as the primary analysis on all primary and secondary outcomes after the last participant has participated in the last visit. Missing values will be handled with a last observation carried forward approach for ITT analysis. Per-protocol (PP) analysis will only be performed in case of sensitivity testing.

Parametric tests (general linear models) will be used to test differences in outcomes from baseline to follow-up. Heterogeneity in responsiveness to the interventions will be tested by dividing each intervention group into smaller groups based on data distribution (medians) or clinically meaningful cut-points. If model assumptions cannot be met even after logarithmic transformation, non-parametric tests will be used. Plots of residuals versus predicted values will be used to judge normality. Metabolic patterns will be tested with multivariate statistics. Adjustment for relevant confounders will be performed. Two-sided tests will be used. *P* values of <0.05 are considered significant. The statistical programs SPSS and SAS will be used for data analysis.

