HbA1c was measured at the screening visit (V0), at the baseline visit (V1), after 12 weeks of intervention, after 24 weeks (V2) of intervention, and after six months follow-up (V3). MAGE was measured after the baseline visit (V1), and after 24 weeks of intervention (after V2).

See section 6: Analyses for timing of secondary and descriptive/explorative outcome assessments.

Section 4: Statistical Principles

Confidence intervals and P values

Two-sided P-values and 95% confidence intervals will be presented for comparisons between groups. Two-sided 95% confidence intervals will be presented for within group comparisons and estimated levels.

Primary outcome: The direction and size of the estimated mean effect for HbA1c and MAGE (primary outcomes), in addition to the 95% confidence intervals, will be required to support the tested hypothesis for the results to be declared in accordance with the hypothesis (see section 2 under “Objectives”).

Secondary outcomes: False detection rate (FDR) correction ad modum Benjamini and Hochberg (16) will be used to control for multiplicity; < 5% will be used as the threshold for FDR.

Completers and protocol deviations

Completers: Participants who participated in an assessment of at least one of the primary outcomes at V2 and/or V3.

Lost to follow-up: Participants who did not participate in assessment of primary outcomes at V2.

Excluded for statistical data analyses: Participants in both study groups dropping out or lost to follow-up before baseline measurements have been collected.

Protocol deviators: None of the participants in the two study groups are considered protocol deviators.

Analysis populations

Efficacy estimates based on intention-to-treat (ITT) analysis set:

All participants will be analysed as randomised.

Section 5: Trial Population

Screening data

The following data obtained at the screening visit will be included for those that entered the trial:

- Age
- Self-reported sex
- Self-reported ethnicity
- Self-reported educational level
- Self-reported smoking status and number of years of smoking
- Diabetes duration

Eligibility

- Age: ≥ 18 to ≤ 75 years
- Diabetes duration: ≥ 12 months
- HbA1c: 53–97 mmol/mol
- Diet or any glucose-lowering medication
- Diagnosed with T2D and treated at Steno Diabetes Center Copenhagen

Recruitment

The flow diagram of the trial will comply with the most recent CONSORT guidelines for Reporting Outcomes in Trial Reports and includes:

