Estimation of minimal important difference for primary outcome: Reductions in HbA1c of 3 mmol/mol and 0.3 mmol/l of MAGE were defined as minimal important differences in this trial. This was primarily based on findings from clinical trials of different dietary approaches for reducing HbA1c in T2D (18, 19). Since no studies had examined the effect of dietary interventions using MAGE as an outcome in our target population with T2D at the time. Thus, based on previous findings (18, 19) we expected to find HbA1c reductions around 3 mmol/mol compared to standard care. This was considered clinically relevant as part of a multidisciplinary approach for the management of hyperglycaemia in T2D.

Secondary/descriptive/exploratory outcomes

The treatment effect will be given as the baseline corrected difference between the groups at V2 and V3. No minimal clinically relevant differences were defined for these outcomes.

- HbA1c (mmol/mol) (only for V3)
- Total body weight (kg), women
- Total body weight (kg), men
- BMI (kg/m²)
- Blood pressure
 - Systolic blood pressure (mmHg)
 - Diastolic blood pressure (mmHg)
- Fasting concentration of plasma lipids
 - Total cholesterol (mmol/l)
 - LDL cholesterol (mmol/l)
 - HDL cholesterol (mmol/l)
- Anthropometry
 - Waist circumference, cm (women)
 - Waist circumference, cm (men)
 - Waist/Hip ratio, unitless (women)
 - Waist/Hip ratio, unitless (men)
- Blinded CGM data (not measured at V3)
 - Mean plasma glucose, mmol/l
 - Time in range (TIR): % of readings and time 3.9-10.0 mmol/l
 - Time above range (TAR): % and readings and time 10.1-13.9 mmol/l
 - Time below range (TBR): % readings and time 3.0-3.8 mmol/l
 - Glycaemic variability, coefficient of variation (CV), %
 - Glycaemic variability, standard deviation (SD), mmol/l
- Numeracy skills test

- Total score
- Correct answers, n and %
- Carbohydrate estimation accuracy test based on 11 high-carb foods (only for foods reported eaten)
 - Estimation errors in %
- Self-reported diabetes diet-related quality of life (DDRQOL), total score within each subscale
 - General perception of diet
 - Satisfaction with diet
 - Restriction of social functions
 - Burden of dietary therapy
 - Perceived benefits of dietary therapy
 - Mental health
 - Vitality
- Self-reported Perceived Health Competence Scale (PCS), total score
- Self-reported Healthcare Climate Questionnaire (HCCQ) (not measured at V3), total score
- Dietary intake (not measured at V3)
 - Total energy intake (kJ/day)

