All continuous outcomes covered by this SAP will as a rule be modelled using baseline corrected repeated measures regression (20) with the following fixed effects and interactions between fixed effects: Visit, Visit (factorial)*Treatment. Data from V1, V2, and V3 will be included in the analysis. The models will be specified with a restricted maximum likelihood estimation method and a repeat on participant level (unstructured covariance structure). Model fit will be evaluated using graphical methods before estimating the treatment effects and if necessary, outcomes will be log-transformed. Estimated mean differences (CI95%) between groups (CI95%), conditional means (CI95%), and within group changes (CI95%) will be extracted from the model. For log-transformed outcomes the results will be back-transformed and be presented as the ratio between estimated mean differences (CI95%), estimated conditional geometric means (CI95%) and relative changes within groups (CI95%), respectively. If distribution assumptions cannot be met by log-transformation, a generalized mixed linear model with an appropriate distribution will be applied instead of the repeated measures regression model. In case the distribution does not comply with the distributions available in the generalized mixed linear model a non-parametric test will be used to compare the change scores for the given outcome.

Missing data

The number/frequency of missing values for the primary outcomes in each group at each time point will be provided. In the primary analysis, missing data are handled implicitly by maximum likelihood estimation in the linear mixed model and missing data will be assumed to be missing at random. This is equivalent to making multiple imputations for each treatment group separately and estimating the treatment effect that would have been found had all subject completed their assigned treatment (efficacy estimate) under the missing at random assumption.

Additional analyses

Not relevant.

Harms

Data on harms are not systematically collected and will not be reported.

Statistical software

SAS Enterprise Guide software version 8.3 or newer (SAS Institute Inc., Cary, NC, USA) and R software version 4.0.2 or newer (R Core Team, R Foundation for Statistical Computing, Vienna, Austria).

References

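### The week-12 HbA1c is measured but has no role in the HbA1c model; adding it is a cheap gain in robustness and, modestly, in precision

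*SAP*

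**What the plan says.** SAP Section 3 (Timing of outcome assessments) lists HbA1c at screening, at baseline (V1) and then "after 12 weeks of intervention, after 24 weeks (V2) of intervention, and after six months follow-up (V3"). SAP Section 6 (Analysis methods) sets out a baseline-corrected repeated-measures model with visit and visit-by-treatment terms, REML and an unstructured covariance, and adds: "Data from V1, V2, and V3 will be included in the analysis". The model applies as a rule to all continuous outcomes; no exception is written for HbA1c. The primary contrast is at V2, and the secondary list has "HbA1c (mmol/mol) (only for V3"). Additional analyses are declared not relevant.

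Under Missing data, "missing data will be assumed to be missing at random", and of the likelihood approach the SAP says: "This is equivalent to making multiple imputations for each treatment group separately". It also promises counts of missing primary-outcome values at each time point, which could include week 12 but would only be a tabulation.

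The protocol numbers its visits differently: its V3 is week 12. Its section 10.2 states "HbA1c will also be measured at the screening visit and visits V2, V3 and V4 in a non-fasting condition", that is, weeks 0, 12 and 20, and section 11.5 repeats the week-12 measurement ("Measurement of body weight and HbA1c (non-fasting condition")). Protocol 13.2 had a different missing-data rule: "Missing values will be handled with a last observation carried forward approach for ITT analysis".

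**The concern.** HbA1c at week 24 is a primary outcome, and Protocol 13.3 plans for about 30% drop-out. Someone who leaves between weeks 12 and 24 and gives no later value enters the planned model with V1 and baseline covariates only. Their week-24 value is then implied by how similar participants at baseline fared in the same arm. How they were doing on treatment at week 12 is ignored, although it was measured.

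The protocol's carry-forward rule could have used that value. Moving to a likelihood model is sound, but the move left week 12 with no role. Two things are at stake: some precision, and the credibility of missing-at-random if people leave because of how they responded in the first 12 weeks. The SAP plans no missing-data sensitivity analysis that would show whether this matters.

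**Working it through.** **1. Which visit is which.** The SAP defines V2 as 24 weeks and V3 as six-month follow-up, so its V3 does not bring in the protocol's V3 (week 12). Week 12 is outside the model.

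**2. The plan's own figure.** For a difference of 3.0, SD 7, two-sided 5% and 80% power, the normal formula gives 2 × (1.96 + 0.842)² × 49/9 = 85.5, so 86 per arm; the t-test version gives 86.4, so 87. The protocol's 87 per arm (174 in total) reproduces, and 174 × 1.30 = 226.

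**3. Inputs.** From the documents: SD of change 7, 113 per arm, about 30% drop-out. Assumed, because the documents give neither: the correlations r(V1,12), r(V1,24), r(12,24), and when people leave. Also assumed: all 113 per arm have V1, and nobody returns after leaving, so V3 adds nothing to the week-24 estimate. Covariates other than baseline HbA1c are left out.

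**4. Precision formula.** Let n24 and n12 be the numbers per arm seen at weeks 24 and 12.
- σ² = 49 / [2(1 − r(V1,24))]
- A = σ²(1 − r(V1,24)²), the week-24 variance given V1
- b = [r(12,24) − r(V1,12) r(V1,24)] / (1 − r(V1,12)²)
- B = b²σ²(1 − r(V1,12)²), the part of A that week 12 explains
- Without week 12: Var = 2A/n24
- With week 12: Var = 2[(A − B)/n24 + B/n12]
- Proportional cut = (B/A)(1 − n24/n12)

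**5. Central set 0.65 / 0.60 / 0.75.** σ² = 61.25, A = 39.2, b = 0.36/0.5775 = 0.623, B = 13.75, B/A = 0.351, n24 = 79.1.
- Without week 12: SE = √(2 × 39.2/79.1) = 0.996.
- 10% leaving after week 12 (n12 = 90.4): SE 0.974; cut 0.351 × 0.125 = 4.4%.
- 20% leaving after week 12 (n12 = 101.7): SE 0.956; cut 0.351 × 0.222 = 7.8%.

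Over seven correlation sets (r(V1,12) 0.55–0.75, r(V1,24) 0.50–0.70, r(12,24) 0.70–0.85) the cut runs from 2.8% to 10.5%. With only 10% or 15% missing, half of it after week 12, the central set gives 1.8% or 2.8%.

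**6. Power and the success rule.** At a true effect of 3, power for p < 0.05 is Φ(3/SE − 1.96): 85.4% without week 12, 86.9% and 88.1% with it. But SAP Section 2 also requires the estimate to reach the minimal important difference, 3 mmol/mol for HbA1c. Significance needs only 1.96 × 0.996 = 1.95, or 1.96 × 0.956 = 1.87, so the 3 mmol/mol condition binds. The chance of success on HbA1c is then Φ((true effect − 3)/SE): 50% at a true effect of 3 whatever the SE, and at a true effect of 4 it goes from Φ(1/0.996) = 84.2% to Φ(1/0.956) = 85.2%.

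**7. Bias.** Large-sample simulation, central set, 20% leaving after week 12, true effect −3 at week 24 and an assumed −2 at week 12. The log-odds of leaving rise by 0.06, 0.12 or 0.20 per mmol/mol of week-12 change. Bias of the model without week 12, in mmol/mol:

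| Dependence on week-12 response | 0.06 | 0.12 | 0.20 |
|---|---|---|---|
| BCC arm only | −0.29 | −0.54 | −0.78 |
| Control arm only | +0.29 | +0.54 | +0.79 |
| Same slope and same overall loss in both arms | 0.00 | 0.00 | 0.00 |
| Opposite slopes in the two arms | −0.58 | −1.09 | −1.59 |

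With 10% leaving, the BCC-only figures are −0.16, −0.31 and −0.46. With week 12 in the model the bias is zero to within simulation error. That follows from the set-up, since the simulated drop-out depends only on the week-12 change.

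**The case against.** The strongest reply is that one three-visit model for every outcome is a defensible choice, and that the gain is small under the SAP's own success rule. Both points stand: step 6 shows that the power gain hardly reaches the declaration of superiority.

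The recoverable group may also be smaller than assumed. Under the SAP, randomisation precedes V1 and those lost before baseline measurement are excluded, so part of the planned 30% may leave where week 12 cannot help. Inflating 174 to 226 covers a loss of only 1 − 174/226 = 23%. Protocol 9.5.3 also allows end-of-study follow-up of withdrawn participants, which gives some of them a V3 value. In addition, week-12 values in the BCC arm may fall before or after the third group session (week 14 ± 21 days); this may weaken the correlation with week 24, but it does not alter the week-24 contrast.

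The bias figures rest on assumed mechanisms. A reader might infer from them that the planned estimate is biased. The documents do not support that: no text says that drop-out depends on week-12 response, still less differently by arm. A reader might also set the error in one participant's implied week-24 value beside the 3 mmol/mol threshold. That threshold is a between-group mean difference, and one participant carries about 1/113 of an arm mean.

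What the reply does not remove is the gap itself: a post-baseline value of a primary outcome is held and has no role in handling missing week-24 values.

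**Conclusion.** The point holds as a low-cost improvement. The text is clear that week 12 is measured and is outside the model; at most it is counted in the missing-value table. The planned REML analysis remains legitimate and is not an error.

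The precision gain is modest: about 3–10% of the variance with 30% missing and 10–20% leaving after week 12, and about 2–3% under lighter drop-out in the central set. The chance of declaring superiority on HbA1c is essentially unchanged. The better reason for the change is robustness: it removes the bias that runs through the week-12 value, some tenths of a mmol/mol or more if drop-out depends on that value differently by arm, and about zero if the dependence is alike in both. The textual finding is firm; every size depends on assumed correlations, drop-out timing and drop-out mechanism.

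**What to change.** For HbA1c only, and before analysis, replace the sentence on included visits in SAP Section 6 with: *Data from V1, week 12, V2 and V3 will be included. Visit and Visit*×*Treatment have one level per visit, with a common mean at V1 and an unstructured covariance. The primary contrast is the group difference at V2 (week 24). If this model does not converge, the three-visit model will be used.*

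State whether the week-0 and week-20 HbA1c values scheduled in the protocol were collected, since the SAP's timing section lists neither. Leave MAGE and all other outcomes as planned.

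The cost is one SAP passage and one extra visit level in one model, with no new data. The covariance matrix grows from 6 to 10 parameters, which 226 participants can support. The convergence fallback makes the choice of model depend on the data, so it should be written down in advance.

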9.3 Interventions

9.3.1 Basic carbohydrate counting intervention

Participants randomized to the BCC intervention group will receive standard dietary care targeted patients with T2D treated in a specialized outpatient diabetes clinic with a BCC program as an addon. The routine dietary care includes one initial individual dietary counselling (60 min) and two individual follow-up counselling sessions (2 x 30 min) by a trained dietitian. The BCC program is described below.

Composition of the BCC program:

- Two 180 min interactive group sessions
- One 120 min interactive follow-up session

The BCC program consists of two sessions of three hours with two weeks in between and a follow-up session of two hours after 10 weeks delivered by trained dietitians. The BCC program is a group-based educational program based on several years of experience with this BCC concept at SDCC. The BCC program uses trained dietitians as educators following a planned curriculum which include experience-based leaning with problem-solving exercises, hands-on activities, short theoretical presentations, discussions of motivational aspects and coping strategies. The BCC program integrates peer modelling, skill development, goal setting, observational learning and social support into the program content and activities. The training includes identifying carbohydrates in food, reading carbohydrate tables, calculating the carbohydrate content from food labels, tables and applications (app) for smartphones and use of a personalized carbohydrate plan with guiding suggestions for daily

intake of carbohydrates at meals based on personal dietary recordings including plasma glucose measurements. An app from the Danish Diabetes Association (*Diabetes og Kulhydrattælling*[®]. The Danish Diabetes Association's app, Pragma soft A/S, available in Google Play[®] and App Store[®] 12/2014, Free) will be introduced to support estimation and calculation of carbohydrates.

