Participants will receive the usual dietary care during the same initial 20 weeks of the intervention as the BCC program (see **Figure 2** for a detailed description of visit flow). After the 20 weeks, the participants are not allowed to receive further dietary education by a dietitian. Participants are encouraged to follow their dietary plan according to their intervention for another four weeks until week 24 followed by a 6-months follow-up period. During the intervention period and follow-up period participants are followed as usual in the diabetes clinic at SDCC or SDCC-Gentofte Hospital for a total of 48 weeks.

The BCC courses will consist of both study participants and patients since the courses are a part of a non-standard nutrition education initiative running at SDCC as a supplement to standard care, funded by the Novo Nordisk Foundation. The courses are targeted patients with T2D treated at SDCC and SDCC-Gentofte Hospital and runs in the period 2018-2020. Close relatives are included in the courses if participants or patients need extra support to manage dietary changes based on an individual assessment by the principle study investigator.

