9.3.2 Control group

Participants randomized to the control group will receive standard outpatient dietary care which includes one initial individual dietary counselling (60 min) and two individual follow-up counselling (2 x 30 min) by a trained dietitian based on the overall treatment goal of reducing HbA1c setting personal dietary goals for behavioural change according to individual patient preferences. Dietary guidance includes topics such as healthy dietary habits and weight loss approaches according to the national food-based dietary guidelines ("*De 10 kostråd*"), replacement of high calorie foods with low calorie foods or special attention to carbohydrate sources (e.g. glycaemic index and dietary fibre intake). Besides the three individual dietary counselling sessions, the participants are not allowed to receive further dietary education by a dietitian. Participants are encouraged to follow their dietary plan for another four weeks until week 24 followed by a 6-months follow-up period. During the intervention and follow-up period participants are followed as usual in the diabetes clinic at SDCC or SDCC-Gentofte Hospital for a total of 48 weeks.

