9.10 Study feasibility

SDCC has the facilities to carry out the study. SDCC has a kitchen for patient education called "FoodLab" designed to carry out group education programs with hands-on activities to practice food and self-management skills related to diabetes e.g. courses in BCC.

Approximately 6,000 patients with T2D are treated at SDCC and SDCC-Gentofte Hospital and only a limited number of these patients have already attended an education program in BCC at SDCC. At least 15 courses in BCC are needed for education of 113 patients in the BCC group based on the assumption that we can recruit eight patients with T2D for each course not taking into account potential relatives and patients participating. During the last four years, 64 patients with T2D have

attended the BCC program at SDCC. We will implement approximately 8 courses per year from 2018 equal to 64 patients per year.

One or two new courses in the BCC program will be initiated every third week at SDCC for patients with T2D except for holiday periods. Patients who do not wish to participate in the study or who do not fulfil the inclusion criteria will be included in the BCC courses together with BCC study participants. Additionally, some relatives will also be offered the opportunity to attend the BCC courses, if patients need extra support to manage dietary changes based on an individual assessment by the principle study investigator.

10 Examinations

All patients found eligible for inclusion in the study will be invited to a first study visit (V1) for collection of baseline measurements up to four weeks before the intervention according to study specific SOPs. Subsequently, all participants will be randomized to one of the two study groups. All examinations will be performed in the outpatient diabetes clinic at SDCC. Study visits and examinations are described in detail in **table 1** below and in the current section and section 11.

Visit no Time, week no from start of intervention	Contact -8 to -4	Scree ning	V1 -4 to -1	V2 0-2	V3 4-12	V4 14-20	V5 24	V6 48	Described in section
Participant-related information									
Study information	Х								9.6
Informed written consent		Х							9.7
Eligible for inclusion		Х							9.7
Randomisation		Х							9.8
Efficacy outcomes									•
HbA1c		Х	Х	Х	Х	Х	Х	Х	10.2
Plasma lipids			Х				Х	Х	10.2
Body weight			Х	Х	Х	Х	Х	Х	10.1
Height			Х						10.1
Blood pressure			Х				Х	Х	10.1
Waist and hip circumference			Х				Х	Х	10.1

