11.4.1. V2A: Start of intervention, day 1 (week 2) (BCC only)

At visit 2A the following procedures will be performed for participants randomized to the BCC group:

• Day 1 of BCC program in groups according to curriculum

This visit will take place ± 14 days compared to V2

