11.5.1. V3A: intervention, day 2 (week 4) (BCC only)

At visit 3A the following procedures will be performed for participants randomized to the BCC group:
Day 2 of BCC program in groups according to curriculum

For logistical reasons the visit will take place ± 21 days compared to V2A

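### BCC is taught in group courses in one arm only, but the analysis model and the sample size treat participants as independent; if outcomes correlate within course, the reported CIs and P values are somewhat too optimistic, mainly for the secondary outcomes

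*SAP*

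**What the plan says.** Participants are randomised individually, 1:1 (Protocol 9.8). Delivery then differs by arm.

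- **BCC arm.** On top of individual counselling, there are two three-hour group sessions and one two-hour group session (Protocol 9.3.1), for example "Day 1 of BCC program in groups according to curriculum" (Protocol 11.4.1). On content, "The BCC program integrates peer modelling, skill development, goal setting, observational learning and social support into the program content and activities" (Protocol 9.3.1).
- **Number of courses.** "At least 15 courses in BCC are needed for education of 113 patients in the BCC group", and "One or two new courses in the BCC program will be initiated every third week at SDCC" outside holiday periods (both Protocol 9.10). The groups are mixed: "The BCC courses will consist of both study participants and patients" (Protocol 9.3.1).
- **Control arm.** "Participants randomized to the control group will receive standard outpatient dietary care which includes one initial individual dietary counselling", with two further individual sessions and no group teaching (Protocol 9.3.2).
- **Model.** SAP Section 6, Analysis methods, has visit and visit-by-treatment effects, adjustment for the stratification variables, and a "restricted maximum likelihood estimation method and a repeat on participant level (unstructured covariance structure". Under Additional analyses the SAP plans nothing.
- **Sample size.** 87 evaluable per arm for 80% power at a difference of 3.0 mmol/mol, SD 7, two-sided 5% (Protocol 13.3).
- **Decision rules.** A primary claim needs P<0.05 and an estimate at or beyond the minimal important difference (SAP Section 2). Secondary outcomes use Benjamini-Hochberg at 5% (SAP Section 4), with no minimal difference defined (SAP Section 6).

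Neither document uses course as a variable, gives an ICC, or says that clustering was considered.

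**The concern.** This is a partially nested design: one arm is grouped after randomisation and the other is not. Peer learning and social support are intended ingredients of the BCC programme, so people in the same course may have more similar outcomes than people in different courses. An unstructured covariance across one participant's own visits cannot absorb correlation between participants.

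If that correlation is positive, the model's standard errors are too small. This applies to the between-group comparisons and, more strongly, to the within-group changes in the BCC arm, which the SAP also reports with 95% CIs. For the secondary outcomes the FDR-adjusted P value is the only test applied, so nothing else guards against an understated standard error.

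**Working it through.** **1. The plan's own figure.** n per arm = 2 × (1.96 + 0.8416)² × 7² / 3² = 85.5, so 86 by the normal formula. The t-test gives 86.4, so 87, as stated. No design effect enters. Power at 87 per arm is 80.7% (normal). MAGE has the same ratio: 0.3/0.7 = 3/7.

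**2. Participants per course.** The documents do not give this, so three cases are taken with 87 evaluable BCC participants:

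- 15 courses (the stated minimum): 87/15 = 5.8, the largest average consistent with that minimum.
- 24 courses (about 8 a year, Protocol 9.10, over 2018-2020, Protocol 9.3.1): 87/24 = 3.6.
- About 39 courses (one every third week over about 117 weeks, from August 2018 to 48 weeks before October 2021, ignoring holidays): 87/39 = 2.2.

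**3. Two-sample test.** With design effect DE = 1 + (m − 1) × ICC in the BCC arm only, the standard error is too small by f = √((1 + DE)/2), and a nominal 5% test runs at 2 × [1 − Φ(1.96/f)]. Example: m = 5.8 and ICC 0.05 give DE = 1.24, f = √1.12 = 1.058, level 6.4%. The ICC values are assumed.

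| Courses | ICC 0.01 | ICC 0.05 | ICC 0.10 |
|---|---|---|---|
| 15 (5.8 each) | 5.3% | 6.4% | 7.8% |
| 24 (3.6 each) | 5.2% | 5.8% | 6.5% |
| about 39 (2.2 each) | 5.1% | 5.4% | 5.7% |

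A simulation with 15 courses of 5 or 6 and an ordinary t-test gave 4.9%, 6.4% and 7.8% at ICC 0, 0.05 and 0.10.

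**4. The SAP's baseline-corrected model.** Read SD 7 as the SD of change and assume a baseline-to-week-24 correlation ρ of 0.4 or 0.6. Then s = 7/√(2(1 − ρ)) and SE = s × √((2(1 − ρ²) + (m − 1)τ)/87), where τ is the course share of week-24 variance (not the same scale as the ICC in step 3). At m = 5.8 the true level is 6.7% (ρ 0.4) or 7.2% (ρ 0.6) at τ = 0.05, and 8.4% or 9.5% at τ = 0.10. It is higher than in step 3 because baseline correction removes variance between participants but not course variance that arises after baseline.

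**5. BCC within-group CIs.** Here the full √DE applies. At 5.8 per course it is √1.24 = 1.11 (ICC 0.05) or √1.48 = 1.22 (ICC 0.10), so simple 95% CIs cover about 92% or 89%.

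**6. Primary decision rule.** The two-sample SE is 7 × √(2/87) = 1.06, so P<0.05 needs an estimate of 1.96 × 1.06 = 2.08 mmol/mol (2.32 after correction at ICC 0.10, 15 courses). The rule requires 3, so the minimal difference binds first. The chance of an HbA1c claim when there is no effect is 1 − Φ(3/(1.06 × f)): 0.24% without clustering, 0.38% at ICC 0.05 and 0.56% at ICC 0.10. Under the model in step 4 it is 0.04-0.08% without clustering and 0.14-0.35% at τ = 0.10.

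**7. Secondary outcomes.** Benjamini-Hochberg at 5%, simulated with no true differences: 44 outcomes assumed, 18 of them the sex-specific ones in SAP Section 6 at half the group size (2.9 per course), the rest at 5.8. The chance of any false finding is about 8% (ICC 0.05) or 12% (ICC 0.10) with independent outcomes, and about 6% or 8% with a common correlation of 0.5.

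**The case against.** The strongest reply is that the effect may be very small. Fifteen courses is a floor, seats are shared with non-study patients, and the start rate in Protocol 9.10 could produce many more courses. A single curriculum, two named educators (Protocol 16.1) and individual counselling for everyone all favour a low ICC. The primary claim is protected by its minimal-difference condition, and the SAP presents the remaining outcomes under a heading that also calls them descriptive and exploratory.

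Most of this stands, and it limits the size and the remedy. It does not remove the point. Uniform teaching lowers the correlation without making it zero, nothing in the documents shows that it was considered, and the secondary outcomes are formally tested with FDR control. Uneven course sizes would push the effect up for a given number of courses.

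Three stronger readings are tempting but unsupported:

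- **Eight evaluable per course.** The eight in Protocol 9.10 are recruited patients. Eight evaluable would mean 87/8, about 11 courses, against a stated minimum of 15.
- **An underpowered trial.** At 15 courses the protocol's unadjusted test falls to 76.1% (ICC 0.05) or 71.9% (ICC 0.10), but that is not the SAP model. Under step 4, power is 88% or 83% at τ = 0.05 and 85% or 77% at τ = 0.10 (ρ 0.4 or 0.6), so only one of the four cases falls below 80%. Under the full superiority rule, at a true difference of 3, the chance of meeting the HbA1c condition is about 50% whatever the clustering.
- **A large FDR failure.** Treating all secondary outcomes as independent and at full group size overstates it: many are analysed separately by sex, and others are plainly related (weight, BMI and waist; the CGM measures).

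**Conclusion.** The point holds in a limited form. The model and the sample size assume independence in an arm taught in groups, so any positive within-course correlation makes the reported CIs and P values too narrow.

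With 87 evaluable per arm, an assumed ICC of 0.01-0.10 and 15 to about 39 courses, a nominal 5% two-sample test runs between 5.1% and 7.8%. Under the SAP's model with 15 courses it could reach 9.5%. Near an ICC of zero the effect is negligible.

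A reader might infer that the primary superiority claim is unsafe. At the planned SDs it is not: the minimal difference binds first. With the corrected SE at 15 courses, P<0.05 would bind first only if the SD exceeded 3/(1.96 × √(2/87) × f), about 9.5 mmol/mol at ICC 0.05 or 9.1 at ICC 0.10. What is exposed is the reported CIs, including those for BCC within-group change, and the secondary conclusions. This is worth correcting before analysis because it is cheap. Confidence is medium, since both the ICC and the group size are assumed.

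**What to change.** - Extract each BCC participant's first assigned course as an analysis variable. Each control, and any BCC participant never assigned to a course, is their own unit.
- Prespecify a sensitivity analysis for the primary outcomes and for any secondary outcome declared significant. It should allow for within-course correlation in the BCC arm after baseline, by a course random effect at SAP V2 and V3 only or by cluster-robust standard errors, with small-sample degrees of freedom.
- Do not use a course intercept shared by all visits, because teaching starts after V1. In a check with 15 courses of 6 and 90 controls, over ρ 0.4-0.6 and τ 0.05-0.10, the ratio of model SE to true SE was 0.85-0.93 with no course term, 0.85-0.94 with a shared intercept and 0.99 with a course effect at V2 only.
- Report the ICC for HbA1c and MAGE, and state that the protocol's 80% power assumes no within-course correlation.

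**Cost.** SAP wording, one variable, and one variance term or robust SEs. For patients who sign up or are referred, the course date is registered in the medical record (Protocol 9.4), but course is not among the listed study data (Protocol 10.8, 14.2), so it must be extracted. Session windows ("For logistical reasons the visit will take place ± 21 days compared to V2A", Protocol 11.5.1) mean the group attended could differ from the first assigned course; the documents do not say whether anyone switched. The downsides are slightly wider CIs and a variance component estimated from few small groups. That is why a sensitivity analysis, rather than a new main analysis, is proportionate.
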